10.5.3 Safety objectives

10.5.3.1 Analysis set and grouping for the analyses

For all safety analyses, the safety set will be used. All listings and tables will be presented by treatment group.

The overall observation period will be divided into three mutually exclusive segments:

1. pre-treatment period: from day of subject's first informed consent to the day before first administration of study treatment
2. on-treatment period: from day of first administration of study treatment to 30 days after last actual administration of the same study treatment (including start and stop date)
3. post-treatment period: starting at day 31 after last administration of any study treatment

Summary tables for safety data will be presented for the on-treatment period. Comparative analysis will be performed only for the on-treatment period. Listings of safety data will include pre-treatment, on-treatment, and post-treatment periods, with a flag to indicate data collected before or after the on-treatment period.

The same analysis will be done for patients that switch to asciminib after treatment failure on bosutinib. However, safety events that initiated on or after start of asciminib during the switch treatment phase will be included.

10.5.3.2 Adverse events (AEs)

Summary tables for adverse events (AEs) will include only AEs that started or worsened during the on-treatment period, the *treatment-emergent* AEs.

The incidence of treatment-emergent adverse events (new or worsening from baseline) will be summarized by system organ class and/or preferred term, severity (based on CTCAE grades), type of adverse event, relation to study treatment.

Serious adverse events, non-serious adverse events and adverse events of special interest (AESI) during the on-treatment period will be tabulated.

[figure not shown]
All deaths (on-treatment and post-treatment) will be summarized.

All AEs, deaths and serious adverse events (including those from the pre-treatment, on-treatment and post-treatment periods) will be listed and those collected before or after the on-treatment period will be flagged.

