6.1.5 Treatment duration

There is no fixed duration of treatment planned per patient. The patients are treated in the study up to end of study treatment period defined as up to 96 weeks after the last patient receives the first dose or up to 48 weeks after the last patient has switched to asciminib treatment whichever is longer unless patients have discontinued treatment earlier. Patients may be discontinued from treatment with the study drug at any time due to unacceptable toxicity, disease progression and/or at the discretion of the investigator or the patient.

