spontaneous miscarriage or in the event of elective abortion, the patient is permitted to continue study treatment.

- In the event of treatment failure the patient must be discontinued from the study treatment. Patients randomized to bosutinib treatment experiencing treatment failure may switch to asciminib treatment. The following events will constitute ‘treatment failure’, and are based on the ELN criteria ([Baccarani et al 2013](#)) defining failure of a second line treatment:
 - No CHR or > 95% Ph+ metaphases at three months after initiation of therapy or thereafter
 - BCR-ABL1 ratio > 10% IS and/or > 65% Ph+ metaphases at six months after initiation of therapy or thereafter
 - BCR-ABL1 ratio > 10% IS and/or > 35% Ph+ metaphases at 12 months after initiation of therapy or thereafter
 - Loss of CHR, CCyR or PCyR at any time after initiation of therapy
 - Detection of new BCR-ABL1 mutations which potentially cause resistance to study treatment (asciminib or bosutinib) at any time after initiation of therapy
 - Confirmed loss of MMR in 2 consecutive tests ([Section 7.2.1.1](#))
 - New clonal chromosome abnormalities in Ph+ cells: CCA/Ph+: at any time after initiation of therapy
- In the event of disease progression the patient must be discontinued from the study treatment. The following events are considered disease progression.
 1. CML-related death (any death during treatment or follow-up if the principal cause of death is marked as “study indication” in the eCRF by the investigator, or if the death occurred subsequent to documented progression to AP/BC and the cause of death is reported as “unknown” or not reported by the investigator)
 2. Accelerated phase (AP) as defined by any of the following:
 - $\geq 15\%$ blasts in the peripheral blood or bone marrow aspirate, but $< 30\%$ blasts in both the peripheral blood and bone marrow aspirate
 - $\geq 30\%$ blasts plus promyelocytes in peripheral blood or bone marrow aspirate
 - $\geq 20\%$ basophils in the peripheral blood
 - Thrombocytopenia ($< 100 \times 10^9/L$) that is unrelated to therapy
 3. Blast crisis (BC) as defined by any of the following:
 - $\geq 30\%$ blasts in peripheral blood or bone marrow aspirate
 - Appearance of extramedullary involvement other than hepatosplenomegaly proven by biopsy (i.e., chloroma).

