10.3 Treatments (study treatment, concomitant therapies, compliance)

The Safety set will be used for the analyses below.

Categorical data will be summarized as frequencies and percentages. For continuous data, mean, standard deviation, median, 25th and 75th percentiles, minimum, and maximum will be presented.

The duration of exposure in days to asciminib and bosutinib, as well as the dose intensity (computed as the ratio of actual cumulative dose received and actual duration of exposure) and

the relative dose intensity (computed as the ratio of dose intensity and planned dose intensity) will be summarized by means of descriptive statistics.

The number of patients with dose adjustments (reductions, interruption, or permanent discontinuation) and the reasons will be summarized by treatment group and all dosing data will be listed.

Concomitant medications and significant non-drug therapies prior to and after the start of the study treatment will be listed and summarized according to the Anatomical Therapeutic Chemical (ATC) classification system, by treatment group.

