10.5 Secondary objectives

The secondary objectives in this study are as follows:

- To compare additional parameters of the efficacy of asciminib versus bosutinib, defined as:

Key secondary endpoints

[figure not shown]
- MMR rate at 96 weeks

Other efficacy endpoints

- Cytogenetic response (Complete, Partial, Major, Minor, Minimal, no response) rate at all scheduled data collection time points including, 24, 48 and 96 weeks.
- Cytogenetic response (Complete, Partial, Major, Minor, Minimal, no response) rate by all scheduled data collection time points including, 24, 48 and 96 weeks.
- MMR rate at all scheduled data collection time points (except 24 and 96 weeks which are already covered by primary and key secondary endpoints)
- MMR rate by all scheduled data collection time points including 24, 48 and 96 weeks.
- Time to MMR
- Duration of MMR
- Time to CCyR
- Duration of CCyR
- Time to treatment failure
- Progression free survival
- Overall survival
- To compare the safety and tolerability profile of asciminib versus bosutinib
- To characterize the PK of asciminib in the CML-CP population

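### Adverse events are compared as incidence over windows that lengthen with time on treatment; exposure-adjusted and common-window displays should be added

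*Combined protocol and SAP*

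**What the plan says.** Safety is a comparative secondary objective in Section 10.5: "To compare the safety and tolerability profile of asciminib versus bosutinib". For adverse events, Section 10.5.3.2 states the measure: "The incidence of treatment-emergent adverse events (new or worsening from baseline) will be summarized by system organ class and/or preferred term". Further breakdowns are by grade, type and relationship. Serious events and AESIs are tabulated over the same period.

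Section 10.5.3.1 says that the on-treatment period extends "from day of first administration of study treatment to 30 days after last actual administration of the same study treatment". The window is therefore tied to each patient's own dosing. The same section confines the contrast between arms to this window: "Comparative analysis will be performed only for the on-treatment period". Section 10.5.3.3 counts laboratory worst grades once per patient over the same period.

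The length of the period is open. Section 6.1.5 says "There is no fixed duration of treatment planned per patient". It closes the treatment period at the later of two dates: one lies 96 weeks beyond the final patient's initial dose, the other 48 weeks beyond the final switch. Section 7.1.6 adds an outcome-dependent end: "In the event of treatment failure the patient must be discontinued from the study treatment". The option to switch exists only for bosutinib failures and closes their bosutinib window.

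Section 10.3 does summarise "The duration of exposure in days to asciminib and bosutinib", with dose intensity, by descriptive statistics. The text reviewed does not link that summary to adverse event incidence. It specifies no person-time rate, common-window analysis or time-to-first-event analysis for adverse events.

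**The concern.** The proportion of patients with at least one event depends on the event rate and on how long each patient is watched. Here the watching time is the treatment time plus 30 days, and treatment time depends on response, tolerability and date of entry. If the arms differ in treatment time, the arm that keeps patients longer has more opportunity to record events, and its incidence rises even when the underlying rates are equal.

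What is at stake is a fair reading of the comparative safety objective, mostly at the 96-week and end-of-treatment analyses in Section 10.7. The primary cut-off falls when every patient has had 24 weeks of treatment or has stopped earlier (Section 10), so patients who entered earlier already contribute longer exposure at that point. A separate exposure table shows that an imbalance exists, but leaves the reader to guess how much of any difference in incidence it explains.

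**Working it through.** **1. The plan's own figures.** The documents state no adverse event rate, discontinuation rate or expected exposure by arm, so there is no planned safety figure to reproduce. The nearest stated figure is the sample size in Section 10.8. Pooled two-proportion formula, 15% v 35%, two-sided 5%, 90% power, 2:1 allocation: 74 + 148 = 222, power 90.3%, odds ratio (0.35/0.65)/(0.15/0.85) = 3.05. All agree with the plan, and this point does not affect them.

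**2. Assumed inputs.** Constant event hazard h = 0.5 per patient-year in both arms. Exponential time on treatment with median 30 weeks in one arm and 60 in the other. Discontinuation hazard d = ln 2 / (median/52):
- 30 weeks: d = 1.2015 per year
- 60 weeks: d = 0.6007 per year

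**3. Incidence by horizon T (years), without the 30-day tail.** I = h/(h+d) × [1 − exp(−(h+d)T)].
- 24 weeks: 0.2939 × 0.5440 = 16.0% v 0.4542 × 0.3983 = 18.1%; gap 2.1 points
- 48 weeks: 0.2939 × 0.7921 = 23.3% v 0.4542 × 0.6380 = 29.0%; gap 5.7 points
- 96 weeks: 0.2939 × 0.9568 = 28.1% v 0.4542 × 0.8689 = 39.5%; gap about 11 points

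The first-event rate per person-time at risk is 50 per 100 patient-years in both arms by construction. Adding the 30-day tail (0.0821 year) to each patient's window gives 1 − exp(−0.5 × 0.0821) × (1 − I), which at 96 weeks is 31.0% v 41.9%; the gap is still about 11 points.

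**4. Sensitivity.** Same formula, but parameterised by the share still on treatment at the horizon, with 10 to 100 first events per 100 patient-years:
- 96 weeks, 90% v 80% retained: incidence ratio 1.04 to 1.06
- 96 weeks, 80% v 60%: 1.10 to 1.14 (38.5% v 34.1% at 30 per 100 patient-years)
- 96 weeks, 70% v 40%: 1.19 to 1.27 (36.4% v 29.0%)
- 96 weeks, 60% v 30%: 1.23 to 1.33 (34.1% v 26.1%)
- 24-week horizon, the same four retention pairs: gaps of 0.2 to 7.0 points

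**5. Does the adjusted rate suffice by itself?** Take an event with identical early risk in both arms: 50% over the first 4 weeks and none later, so h = ln 2/(4/52) = 9.011 in that window. Keep medians of 30 v 60 weeks.
- Crude incidence: 48.0% v 49.0%, nearly equal, as it should be.
- Person-time at risk without a cut-off: 0.433 v 0.849 years per patient, so 0.480/0.433 = 111 v 0.490/0.849 = 58 per 100 patient-years.
- With a 96-week cut-off: 0.387 v 0.575 years, so 124 v 85 per 100 patient-years.

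Here crude incidence is right, and the adjusted rate falsely favours the longer-treated arm.

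**The case against.** The strongest reply has four parts.

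*Unequal exposure is inferred.* This stands as a limit on the claim. A reader might infer that asciminib is bound to be treated longer and so penalised. The documents do not support that. Section 10.8 assumes a difference in MMR, but missing MMR is not itself a treatment failure under Section 7.1.6, so 15% v 35% does not translate into retention. Some mandatory stops pull the other way: for unspecified grade 4 non-hematologic reactions, Table 6-2 requires permanent discontinuation on asciminib but a hold and dose reduction on bosutinib. Asciminib as the longer-treated arm is likely, not established.

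*Exposure is reported, and incidence is not the only safety output.* Both are true. Grades, relationship, deaths, laboratory shifts, QT categories and dose changes are also summarised. But none of these supplies a person-time or common-time comparison, and the exposure summary reveals an imbalance without correcting for it.

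*The effect is small when it matters most.* This stands in part. A reader might use h/(h+d) without a cut-off and quote 29% v 45% for the 30 v 60 week case. That assumes unlimited follow-up, whereas the plan has defined cut-offs; the gap is about 2 points at a 24-week horizon and 11 at 96 weeks, not 16.

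*Adjusted rates can reverse the bias.* This stands, as step 5 shows. Section 2.2 reports diarrhea in 78.5% and vomiting in 37.1% on bosutinib. Onset timing is not given, but if such events cluster early, rates per patient-year would understate them in the longer-treated arm. A reader might conclude that between-arm statements should rest on adjusted rates; the calculation does not support that.

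Finally, the text reviewed is one part of a longer file, and Section 10.6.2 refers to an SAP for other details. Silence here does not prove that the full SAP is silent.

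**Conclusion.** The point holds as a cheap improvement. The plan commits to comparing the arms on incidence over a window that lengthens with each patient's exposure, and the text reviewed offers no measure that separates rate from exposure. At equal rates, the longer-treated arm shows the higher incidence in every scenario tried: ratios of 1.04 to 1.33 across the 96-week retention scenarios, and 28.1% v 39.5% in the main illustration.

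All these sizes rest on assumed constant hazards and assumed retention; none comes from the documents. The size depends on the actual exposure difference and vanishes if there is none.

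A reader might infer that the safety comparison is invalid or that error control is compromised. Neither follows. Adverse event summaries are descriptive; no hypothesis test, alpha or decision rule depends on them, and onset and dosing dates are collected, so nothing is lost irretrievably.

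**What to change.** In Section 10.5.3.2, keep crude incidence and add, for all adverse events, grade 3 or higher, SAEs and AESIs:

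- (a) patients with a first event per 100 patient-years at risk, with 95% CI, by arm;
- (b) either incidence in a common window, for example the first 24 weeks, or the cumulative incidence of first event with discontinuation as a competing event.

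State that between-arm differences will be interpreted from these together. The rates in (a) assume a roughly constant hazard and understate early-onset events in the longer-treated arm. The displays in (b) place both arms on the same time scale, but still carry some effect of earlier discontinuation (2.1 points at 24 weeks in the illustration).

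The cost is SAP wording and extra tables. Adverse event start dates (Section 8.1.1) and dosing dates (Section 6.7.3.1) are already recorded; conduct, dosing and sample size do not change. If a part of the SAP not seen here already specifies such analyses, a cross-reference from Section 10.5.3.2 is enough.

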10.5.3.3 Laboratory abnormalities

Grading of laboratory values will be assigned programmatically as per NCI Common Terminology Criteria for Adverse Events (CTCAE) version 4.03. The calculation of CTCAE grades will be based on the observed laboratory values only, clinical assessments will not be taken into account.

CTCAE Grade 0 will be assigned for all non-missing values not graded as 1 or higher. Grade 5 will not be used.

For laboratory tests where grades are not defined by CTCAE v4.03, results will be categorized as low/normal/high based on laboratory normal ranges.

The following listings and summaries will be generated separately for hematology, and biochemistry tests:

- Listing of all laboratory data with values flagged to show the corresponding CTCAE v4.03 grades if applicable and the classifications relative to the laboratory normal ranges

For laboratory tests where grades are defined by CTCAE v4.03

- Worst post-baseline CTCAE grade (regardless of the baseline status). Each patient will be counted only once for the worst grade observed post-baseline in the on-treatment period.
- Shift tables using CTCAE grades to compare respective baseline to the worst on-treatment value

For laboratory tests where grades are not defined by CTCAE v4.03,

- Shift tables using the low/normal/high/ (low and high) classification to compare respective baseline to the worst on-treatment value.

10.5.3.4 Other safety data

ECG

ECGs (12-lead) including PR, QRS, QT, QTcF, and HR intervals will be obtained for each subject during the study. ECG data will be read and interpreted centrally.

Categorical analysis of QT/QTc interval data based on the number of patients meeting or exceeding predefined limits in terms of absolute QT/QTc intervals or changes from baseline will be presented. In addition, a listing of these patients will be produced by treatment group.

Vital signs

Data on vital signs will be tabulated and listed, notable values will be flagged.

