To compare additional parameters of the efficacy of asciminib versus bosutinib	
 ● Cytogenetic response rate (Complete, Partial, Major, Minor, Minimal, no response) at and by all scheduled data collection time points including 24, 48 and 96 weeks ● MMR rate at all scheduled data collection time points (except 24 and 96 weeks which are already covered by primary and key secondary endpoints) ● MMR rate by all scheduled data collection time points including 24, 48 and 96 weeks ● Time to MMR ● Duration of MMR ● Time to CCyR ● Duration of CCyR ● Time to treatment failure ● Progression free survival ● Overall survival 	Refer to Section 10.5.2
To compare the safety and tolerability profile of asciminib versus bosutinib	Type, frequency and severity of adverse events, changes in laboratory values that fall outside the pre-determined ranges and clinically notable ECG and other safety data (vital signs, physical examination)	
To characterize the PK of asciminib in the CML-CP population	Trough plasma concentrations, PK parameters in full PK group: C _{max} , T _{max} , AUC _{0-12h} , CL/F	
To assess the safety of asciminib when administered as treatment after bosutinib failure according to the 2013 ELN Guidelines	Type, frequency and severity of adverse events, changes in laboratory values that fall outside the pre-determined ranges and clinically notable ECG and other safety data (vital signs, physical examination)	Refer to Section 10.6

Objective	Endpoint	Analysis
Exploratory		
To evaluate the influence of factors such as cytogenetic response at baseline, failure/intolerance to prior TKIs, line of therapy, gender, race and age on the effect of asciminib with respect to the primary efficacy endpoint	Major Molecular Response (MMR) rate at 24 weeks	Refer to Section 10.6
To explore the exposure-response relationships of asciminib; evaluate the effect of population covariates	Exposure-safety and exposure-PD analyses	
To characterize mutations in the BCR-ABL1 gene at Week 1 Day 1, upon confirmed loss of molecular response and/or at end of treatment and examine their association with molecular and cytogenetic response for asciminib vs. bosutinib	BCR-ABL1 gene mutations at Week 1 Day 1, upon confirmed loss of molecular response and/or at end of treatment as determined by Sanger Sequencing	
[REDACTED]	[REDACTED]	

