7.2.2.6 Cardiac assessments

7.2.2.6.1 Electrocardiogram (ECG)

After the subject has rested approximately 10 minutes in a semi-supine position, standard 12-lead ECGs must be obtained in triplicate with a recommended minimal interval of 5 minutes

between each ECG at the time points specified in [Table 7-1](#), [Table 7-2](#), [Table 7-6](#) and [Table 7-7](#). ECGs should be taken before blood samples for PK if both assessments are scheduled at the same time point. In this case recording of ECGs should be planned according to the true time of blood sample for PK rather than to the scheduled time point.

Table 7-6 Central ECG collection (all patients)

Week (or Day)	Number of ECGs (per visit)	Time of ECG
Screening/Baseline Day -21 to -1 / S-Screening/S-Baseline Day -42 to -1 (all patients)	3	3 serial ECGs at the screening visit
Week 1 Day 1 / S-Week 1 Day 1 (all patients)	3	3 serial ECGs at 2 h post dose
Week 2 Day 1 / S-Week 2 Day 1 (asciminib/asciminib switch patients)	12	3 serial ECGs pre-dose and at 2, 3, 4 h post-dose
Week 2 Day 1 / S-Week 2 Day 1 (bosutinib)	3	3 serial ECGs pre-dose
Week 4 / S-Week 4 (all patients)	3	3 serial ECGs pre-dose
Week 12 / S-Week 12 (all patients)	3	3 serial ECGs pre-dose
Week 24 / S-Week 24 (all patients)	3	3 serial ECGs pre-dose
Week 96 / S-Week 96 (all patients)	3	3 serial ECGs 30 min* post-dose
Unscheduled (all patients)	3	3 serial ECGs
* 30 min +/- 5min allowed		

Table 7-7 Central ECG collection plan for patients in full PK asciminib group

Week (or Day)	Number of ECGs (per visit)	Time of ECG
Day -21 to -1	3	3 serial ECGs at the screening visit
Week 1 Day 1	3	3 serial ECGs at 2 h post dose
Week 2 Day 1	24	3 serial ECGs pre-dose and at 1, 2, 3, 4, 6, 8, 12 h post-dose
Week 4	3	3 serial ECGs pre-dose
Week 12	3	3 serial ECGs pre-dose
Week 24	3	3 serial ECGs pre-dose
Week 96	3	3 serial ECGs 30 min* post-dose
Unscheduled	3	3 serial ECGs
* 30 min +/- 5min allowed		

All ECGs performed will be independently reviewed. Instructions for the collection and transmission of these ECGs to the independent central reader (ERT (Electronic Research Technology, Inc.)) will be provided in the [\[CABL001A2301 ECG Manual\]](#).

Three serial ECGs (triplicate) should be performed ½ hour prior to dosing for pre-dose assessment. The serial ECGs should be taken approximately 5 minutes apart. All 3 ECGs for each time point should be sent to ERT. Readings for QTc prolongation will be based on the

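### Asciminib patients have 9 or 13 scheduled on-treatment ECG time points against 6 for bosutinib, so a by-arm count of patients with QTc outliers needs a time-matched version

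*Combined protocol and SAP*

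**What the plan says.** Table 3-1 lists among the secondary objectives "To compare the safety and tolerability profile of asciminib versus bosutinib", with ECG findings among its endpoints. Section 10.5.3.1 sets the window: "Summary tables for safety data will be presented for the on-treatment period", and "Comparative analysis will be performed only for the on-treatment period". Section 10.5.3.4 then rests the categorical QT analysis on the "number of patients meeting or exceeding predefined limits in terms of absolute QT/QTc intervals or changes from baseline", with a listing of those patients by treatment group. It states no rule on which time points count, on unscheduled ECGs, or on matching between arms.

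The ECG schedule is in Section 7.2.2.6.1. Table 7-6 has one row for "Week 2 Day 1 / S-Week 2 Day 1 (asciminib/asciminib switch patients") with triplicates pre-dose and at 2, 3 and 4 h, and another for "Week 2 Day 1 / S-Week 2 Day 1 (bosutinib") with pre-dose triplicates only. For the full-PK asciminib group, Table 7-7 gives "3 serial ECGs pre-dose and at 1, 2, 3, 4, 6, 8, 12 h post-dose" on that day. The other scheduled on-treatment ECGs are the same in both arms: Week 1 Day 1 ("3 serial ECGs at 2 h post dose"), Weeks 4, 12 and 24 pre-dose, and Week 96 at 30 minutes post-dose. The same section bases QTc readings on the average of the triplicate, so the time point is the unit of measurement.

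**The concern.** The asciminib schedule contains every bosutinib time point plus 3 or 7 more. A patient-level count of ever exceeding a limit can only stay the same or rise as readings are added, whatever the event rate. The extra readings are all post-dose, and several lie near asciminib's median time to peak of 2 to 3 hours (Section 1.2.1.2). Bosutinib's scheduled ECGs after Day 1 are pre-dose, apart from Week 96. A table that pools everything on treatment would set repeated post-dose asciminib readings against mostly pre-dose bosutinib readings. It could not show a bosutinib post-dose effect at Week 2. What is at stake is how a descriptive between-arm QT comparison under a secondary objective is read.

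**Working it through.** **The plan's own figures.** ECGs per visit at Week 2 Day 1 are 3 per time point times the number of time points: 3 × 4 = 12 (sparse PK), 3 × 8 = 24 (full PK) and 3 × 1 = 3 (bosutinib). All three match Tables 7-6 and 7-7.

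**Time points per patient** (W1D1 + W2D1 + W4 + W12 + W24 + W96):

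- Bosutinib: 1 + 1 + 1 + 1 + 1 + 1 = 6
- Asciminib, sparse PK: 1 + 4 + 1 + 1 + 1 + 1 = 9
- Asciminib, full PK: 1 + 8 + 1 + 1 + 1 + 1 = 13

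Through Week 24 the counts are 5, 8 and 12.

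**Share ever flagged, equal and independent risk.** The documents give no risk per time point, so p is an assumption and is shown over a range. Share flagged = 1 − (1 − p)^k, with k = 6, 9 or 13. The asciminib arm is averaged over the 148 planned patients (Section 10.8), with 20 in the full-PK group (the stated minimum, Section 7.2.3) and 148 − 20 = 128 in the sparse group. For example, at p = 0.5%: (128 × 4.41 + 20 × 6.31) / 148 = 4.67%.

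| p | Bosutinib (6) | Sparse (9) | Full PK (13) | Asciminib arm | Ratio of arms |
|---|---|---|---|---|---|
| 0.1% | 0.60% | 0.90% | 1.29% | 0.95% | 1.59 |
| 0.5% | 2.96% | 4.41% | 6.31% | 4.67% | 1.58 |
| 1% | 5.85% | 8.65% | 12.25% | 9.13% | 1.56 |
| 2% | 11.42% | 16.63% | 23.10% | 17.50% | 1.53 |

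In patients, the excess at p = 0.1% is (0.95 − 0.60)% × 148 = 0.5. At p = 1% it is (9.13 − 5.85)% × 148 = 4.9.

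**Within-patient correlation.** Readings in one patient are not independent. A simulation of one million patients used a normal variable with a shared patient effect, p = 1% per time point and a common correlation between all time points (assumed).

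| Correlation | Bosutinib | Asciminib arm | Ratio |
|---|---|---|---|
| 0.3 | 5.29% | 7.82% | 1.48 |
| 0.5 | 4.60% | 6.44% | 1.40 |
| 0.7 | 3.65% | 4.80% | 1.31 |
| 0.9 | 2.37% | 2.81% | 1.19 |
| 1.0 | 1.01% | 1.01% | 1.00 |

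The extra readings all fall on one day, so correlations towards the high end are the more plausible for them.

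**After matching.** Limited to W1D1 2 h, W2D1 pre-dose and Weeks 4, 12, 24 and 96, each arm has 6 time points. With equal risk the ratio is 1.0.

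**The case against.** - **The counting rule is inferred.** Section 10.5.3.4 does not say that each patient is counted over all on-treatment ECGs. The laboratory section (10.5.3.3) does state a once-per-patient, worst-grade rule, and the ECG section has no such sentence. The limits and any time-point rule could be in analysis-plan text not available here. This stands, so the point rests on the natural reading of 10.5.3.1 with 10.5.3.4.
- **The direction may not be net.** A reader might infer that the whole QT comparison is biased against asciminib. The documents do not support that. Drugs with torsades risk are on asciminib's prohibited list (Section 6.4.3, Table 14-1) but are to be used with caution on bosutinib (Section 6.5.1, Table 14-4). That difference could raise bosutinib outliers. Only the ascertainment component has a known direction.
- **The size may be small.** Section 1.2.1.2 reports no QT prolongation by its criteria at 40 mg BID monotherapy. If the risk is about 0.1% per time point, the excess is about half a patient. Thirteen time points apply only to the full-PK group. This stands as a limit on absolute size; less extreme limits would be crossed more often.
- **Matching could hide an asciminib effect.** With Tmax at 2 to 3 hours and accumulation ratios of 1.3 to 2.5, limiting the table to common time points removes every scheduled near-peak asciminib ECG after Day 1. This is a sound reason not to replace the all-ECG table. It does not count against adding a matched one.
- **No test is affected.** The QT analysis is descriptive, and overstating the experimental drug's risk is conservative. Both are true. A reader might also infer a consequence for labelling, but nothing in the documents establishes one.

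**Conclusion.** The concern holds in a limited form. The schedule counts of 6, 9 and 13 are exact. If patients are counted for exceeding a limit at any time on treatment, equal QT behaviour would give a higher asciminib count through measurement frequency alone. The ratio is about 1.5 to 1.6 under independence for assumed risks of 0.1% to 2%. At an assumed 1% risk it falls to about 1.2 at correlation 0.9, and it reaches 1.0 only at correlation 1. The documents fix neither the risk nor the correlation. This is an ascertainment bias in a descriptive comparison. It affects no p-value, and it does not settle the net direction of all biases. It merits a cheap addition to the tables, not a replacement of the planned analysis.

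**What to change.** In Section 10.5.3.4:

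1. Keep the all-ECG on-treatment outlier table and the patient listing. Footnote the table with the number of scheduled time points per arm (6; 9 or 13).
2. Add a between-arm categorical QT/QTcF table limited to the scheduled time points common to both arms: W1D1 2 h, W2D1 pre-dose, and Weeks 4, 12, 24 and 96. State that this is the table for the arm comparison.
3. Report asciminib's extra Week 2 Day 1 time points, and the unscheduled ECGs, separately by arm.
4. If a matching rule already exists elsewhere in the analysis plan, a cross-reference is enough.

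The cost is one programming filter and a footnote. It needs no new ECGs and drops no safety data. The drawback is that the matched table has no scheduled near-peak asciminib ECG after Day 1, so it must be read beside the all-ECG table. It also cannot supply the bosutinib Week 2 post-dose readings that were never scheduled. Recruitment closed on 22-Oct-2019 (Amendment 03-US.01), so that gap can only be disclosed.
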